**REVISION HISTORY**

Revision #	Version Date	Summary of Changes	Consent Change?
1	09/08/22	Addressed track changes and comments	Yes

## Study Summary

Study Title	The Effects of a Gamified Rehabilitation Protocol Compared to an At-Home Exercise Packet in Individuals with Low Back Pain
Study Design	Randomized Controlled Trial
Primary Objective	To measure the change in pain and disability before, during and after a competitive home exercise program compared to a take home packet exercise program.
Secondary Objective(s)	
To quantify adherence and compliance of individuals completing a competitive, gamified home exercise program compared to a traditional autonomous exercise program.
 
To measure the change of Ultrasound thickness and onset of muscle activation of the lateral abdominal wall in individuals with non-specific low back pain during static and exercise positioning following a 6-week home exercise program

Research Intervention(s)/Investigational Agent(s)	None
IND/IDE #	N/A
Study Population	
Individuals aged 18-45 with non-specific low back pain
 
Inclusion Criteria: ages 18-45, biological sex of Male or Female, self-reported low back pain within the previous 6 months or greater than 3 episodes within the past 3 years
 
Exclusion Criteria: Currently seeing and or receiving care from an athletic trainer, physical therapist, or other rehabilitation specialist in the previous 6 months, low back pain conditions such as lumbar spondylosis, herniated disc, spondylolisthesis, previous spine surgery, currently pregnant, experiencing neurological symptoms or other muscular abnormalities.
 
Unable to assume the exercise starting position.
 
Current use of lidocaine patches or prescription pain medicine.

Sample Size	40
Study Duration for individual participants	6-week intervention + 12, 18, 24-month follow-ups
Study Specific Abbreviations/ Definitions	NSLBP: non-specific low back pain; ODI: Oswestry Disability Index; NPRS; Numeric Pain Rating Scale; SUS: System Usability Scale; EARS: Exercise Adherence Rating Scale; CES: Credibility and Expectancy; PCS: pain catastrophizing scale; PBP: Prone Bridge Plank; GROC; Global Rating of Change Scale; TESP: Torso Elevated Side Plank; FESP: Foot Elevated Side Plank; TrA: Transverse abdominis; IO: Internal oblique; EO: External oblique

## Objectives\*

The purpose of the study is to measure the change in pain and disability, quantify adherence and compliance before, during and after a competitive home exercise program compared to a traditional home exercise program. Additionally, to measure the change of ultrasound thickness of the lateral abdominal wall before and after a competitive home exercise program compared to a take home packet exercise program.

We hypothesize that the individuals in the gamified, competitive home exercise program will have decreased pain and disability, increased adherence and increased lateral abdominal wall activation compared to the traditional home exercise program during and after the 6-week protocol.

## Background\*

Non-specific low back pain (NSLBP) can be defined as low back pain with the absence of a known cause. NSLBP diagnoses are concluded when all other pathologies (specific spinal pathology and radicular syndrome) are excluded. In the primary care setting, 90-95% of all low back cases are non-specific. Individuals of all ages experience NSLBP and are affected at a societal level and personal level. Recent recommendations to decrease low back pain include exercise interventions such as trunk strengthening and endurance, trunk muscle activation, aerobic exercise and multimodal interventions. Other guidelines recommend maintaining a physically active lifestyle. In many cases, maintaining a physically active lifestyle requires exercises to be completed at home via prescribed home exercise programs. In order for the efficacy of the home exercise program to be achieved, consistent exercise adherence must occur. Individuals who adhere to their exercise programs have a greater increase in physical function compared with those who have a lack of adherence. Unfortunately, up to 70% of individuals who suffer from chronic low back pain do not adhere to prescribed home exercise.

The lateral abdominal wall is commonly evaluated in individuals that experience NSLBP. The transverse abdominis, internal oblique and external oblique create the lateral abdominal wall. In individuals with NSLBP, the onset of activity of the deep abdominal muscles is delayed. The use of ultrasound imaging can measure the onset of muscle activation as well as muscle thickness of the lateral abdominal wall. Ultrasound imaging is a non-invasive method to visualize and measure muscle thickness. Images can be

produced during static (non-moving) and functional (moving) positions, demonstrating the change in muscle thickness during rest and during movement. Muscle thickness can be obtained during brightness-mode (B-mode) and Motion-mode (M-mode) by measuring the distance between fascial borders (outward tissue layer of the muscle). M-mode ultrasound is unique as it can also detect the onset of muscle activation. Ultrasound imaging can be implemented to understand trunk strengthening, endurance as well as trunk activation to complement the previous recommended guidelines for decreasing low back pain.

Preliminary data includes muscle activation of the rectus abdominis, middle trapezius, middle deltoid, external oblique (EO), erector spinae, gluteus medius, latissimus dorsi during the prone bridge plank (PBP), torso elevated side plank (TESP), and foot elevated side plank (FESP) completed until discontinuation. The rectus abdominis and external oblique elicited moderate to high activation during the 3 exercises. This preliminary data also included subjective measures of reasoning of termination, and in relevance to the present study, only 5.8% of individuals terminated the TESP due to back pain.

General exercise that includes trunk strengthening and endurance, trunk muscle activation, and multimodal interventions are recommended for individuals with NSLBP. Sixty six percent of people who seek treatment for low back pain will have a reoccurrence in the same year. Individuals may not seek additional medical treatment due to time and financial constraints. The implementation of home exercise has increased tremendously over the past years, allowing individuals to stay active in the comfort of their home.

- 3.3 Specifically, exercises such as the PBP, TESP, FESP, dead bug, and bird dog are commonly used to target the muscles of the core and aid in progression of rehabilitation. Although the implementation of home exercise has increased, exercise adherence remains to be an issue. A lack of adherence influences the effects of outcomes in research as well as patient-oriented outcomes such as pain and disability. With up to 70% of individuals not adhering to their prescribed home exercise programs, home exercise methodology must change to increase adherence and decrease pain and disability. Although home exercise has increased in the past years, exercise duration and intensity has decreased. Duration and intensity of exercise may increase by focusing on task and ego-oriented goals. Individuals can focus on the

proper completion of the exercise as well as their performance compared to others. The implementation of a gamified, competitive home exercise program may increase the efficacy and adherence to home exercise while decreasing pain and disability in the NSLBP population. The use of a leaderboard creates a “game” between the participants as they are comparing their hold times to the average and top hold times of others. A leaderboard that includes exercise average hold times, top hold times and reference values, creates a competitive environment with the participants goal to increase their exercise hold times.

### **Study Endpoints\***

For this study, the endpoint is defined as collecting 40 NSLBP individuals.

N/A

N/A

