**Consent and Screening: (~15-20min)**

Informed consent will be obtained for all subjects as outlined in the consent process selection for this protocol. The informed consent document will ask the participant to self-report any exclusion criteria that is listed. After obtaining informed consent, subjects will fill out a questionnaire asking previous and current health history (health history form). Demographic information will also be collected at this time, including, age, sex, height, and weight (basic demographic form) . Participants will also complete questionnaires asking about their low back pain (NumericPainRatingScale\_Question), disability (ODI2.1a\_QuestionnairesRCTLBP), credibility and exercise expectancy (CEQ\_questionnairesRCTLBP), Pain Catastrophizing questionnaire (PCS\_QuestionnairesRCTLBP) and fear avoidance beliefs (FABQ\_QuestionnairesRCTLBP). The remaining study procedures will begin immediately after eligibility determination or subjects can return at another date to complete the remainder of the study procedures. Consent, questionnaires, and surveys will be collected using REDCap.

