#### Patient Reported Outcomes (Subjective Questionnaires)

Each group will be completing the ODI, NPRS, CEQ, FABQ, PCS, Hooper and MacKinnon and Pain Catastrophizing questionnaire at baseline, after 3 weeks and after 6 weeks.

The SUS, EARS will be completed after 3 weeks and 6 weeks.

The GROC will be completed after the 6th week. All questionnaires will be completed again through REDCap at the 12, 18, and 24-month time points.

Lateral abdominal wall muscle thickness will be collected during the baseline session and during the last exercise session of the 6th week.

**6.4 Data collected during the study will include the ODI, NPRS, CEQ, FABQ, Hooper and MacKinnon and PCS questionnaire at baseline, after 3 weeks and after 6 weeks. The SUS, EARS will be completed at 3 weeks and 6 weeks. The GROC will be completed after the 6th week. All questionnaires will be**

completed again through emails notification for participants to complete through REDCap.

6.5 All questionnaires will be completed again through REDCap at the 12, 18, and 24-month time points.

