## **12.0 Local Number of Subjects**

12.1 Based on previous research regarding home exercise and disability with low back pain we determine that 40 participants (20 in each group) will be necessary, alpha set *a priori* to .05. 40 participants include a 15% attrition rate.

12.2 A total of 34 individuals (17 per group) will be adequate with 80% power at an alpha level of .05. We include a 15% attrition rate which results in a total sample size of 40 individuals, 20 in each group

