## **17.0 Data Management\* and Confidentiality**

17.1 For this study, the endpoint is defined as based on previous research regarding home exercise and disability with low back pain we determine that 40 participants (20 in each group) will be necessary, alpha set *a priori* to .05. 40 participants include a 15% attrition rate. Descriptive statistics will be used for age, height, mass. Mean differences, confidence intervals and effect sizes will be used to analyze questionnaires. An activation ratio will be used for the lateral abdominal wall measurements. The static positioning measuring will be used as the numerator and the exercise starting position will be used at the denominator to calculate a ratio.

17.2 All computers storing electronic data will be password protected and only study team members will have access to the passwords. Computers will always remain behind locked doors when not supervised by study team members. All external hard drives used to back up storage will be password protected. Only study team members will have access to these passwords. These passwords will be changed frequently and will be changed immediately if compromised at any point in time.

Participant numbers will be generated by using the IRB # and will be assigned a number (i.e. IRB#12345\_001) as they are enrolled in the study. This number will be utilized in place of any other identifier for the remainder of the study.

Identifiers with de-identified coding will be stored electronically on Redcap and will be deleted after a minimum of 5 years from the time the study closes.

17.3 To ensure quality control of collected data, the 7 exercises performed by participants at their home setting will be demonstrated and taught during the first exercise session with the researcher. Weekly video calls through zoom and emails will be conducted to answer any comments or concerns regarding the exercise completion. We will get in touch with the participants weekly either using zoom (video call) or by email to answer any comments or concerns regarding the exercise completion. The participants email will be provided to the principal investigator when they email showing interest in the study. The leaderboard group will have on demand video that can be accessed at any time and the control take-home packet group will have a packet with pictures and descriptions of the exercises.

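### The endpoint is defined as a recruitment total: pain and disability are not ranked, no primary visit is named, and the 80% power has no stated inputs

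*Combined protocol and SAP*

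**What the plan says.** **Endpoint.** Section 4.0 (Study Endpoints) consists of one sentence, "For this study, the endpoint is defined as collecting 40 NSLBP individuals", followed by two N/A entries. Section 17.1, which holds the analysis text, says that "the endpoint is defined as based on previous research regarding home exercise and disability with low back pain" and goes on to the sample of 40.

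**Objective and hypothesis.** The primary objective in the Study Summary is "To measure the change in pain and disability before, during and after a competitive home exercise program", compared with the take-home packet. Adherence and ultrasound measures are secondary. Section 2.0 gives a direction: the leaderboard group is expected to do better than the packet group on pain, disability, adherence and abdominal wall activation, during and after the six weeks.

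**Instruments and visits.** Section 6.0 (Consent and Screening) links pain to the NPRS and disability to the ODI. Both are collected at baseline, week 3 and week 6, and then "All questionnaires will be completed again through REDCap at the 12, 18, and 24-month time points".

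**Analysis.** Section 17.1: "Mean differences, confidence intervals and effect sizes will be used to analyze questionnaires".

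**Sample size.** Section 12.1: "Based on previous research regarding home exercise and disability with low back pain we determine that 40 participants" are needed. Section 12.2: "A total of 34 individuals (17 per group) will be adequate with 80% power at an alpha level of .05", raised to 40 for 15% attrition.

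**Timing.** Section 9.1 expects the study and its primary analyses to be finished within 8 months of the start of enrollment. It also plans questionnaires 12, 18 and 24 months after the intervention.

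**The concern.** A recruitment total is reached whatever the intervention does, so it cannot be the result on which the trial is judged. Because this is the definition the protocol gives, and section 17.1 repeats the same kind of statement, the defect is a wrong definition and not just a brief one.

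The rest of the document narrows the field without closing it. A reader can work out who is compared with whom and on which two scales. The reader cannot tell which scale decides, at which visit, whether change or final value is compared, by what test, or what counts as success. Followed as written, the plan lets the deciding outcome and visit be chosen after the data are seen, and that cannot be repaired later. The stated alpha of .05 and power of 80% also cannot be checked, because their meaning depends on a rule and on inputs that are not given.

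**Working it through.** **1. Reproduce the plan's figure.** 34 / (1 − 0.15) = 40 and 17 / 0.85 = 20 per group, so the step from 34 to 40 is correct. The 34 itself cannot be reproduced, because section 12 gives no effect size, SD, test or sidedness.

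**2. What 17 per group implies.** Assume a two-sample t-test with 32 degrees of freedom and noncentrality d × √(n/2) = d × √8.5 = 2.915d. The two-sided .05 critical value is 2.037.
- 80% power needs d = 0.991 (noncentrality 2.889). The normal approximation gives (1.960 + 0.842) × √(2/17) = 0.961. A one-sided t-test needs 0.871.
- Two-sided power at illustrative values: d = 0.5 (noncentrality 1.458), 29.3%; d = 0.8 (2.332), 61.9%; d = 0.9 (2.624), 72.1%; d = 1.0 (2.915), 80.7%.

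**3. Is 34 specific to one comparison?** No. A group-by-time F test has noncentrality f² × N × m / (1 − ρ). With assumed f = 0.25, ρ = 0.5 and m = 2 time points this is 0.0625 × 34 × 2 / 0.5 = 8.5, giving 80.7% power. With m = 3 it is 12.75, giving 88.8%. More than one comparison is compatible with 34, so the number does not reveal which was meant.

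**4. How many comparisons stay open?** The intervention lasts 6 weeks, about 1.5 months, so the earliest 12-month questionnaire falls at about 1.5 + 12 = 13.5 months, after month 8. If the 8-month date governs the primary analyses, weeks 3 and 6 remain: 2 outcomes × 2 visits = 4 candidates.

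**5. Conditional false-positive chance.** Assume that each comparison is tested at .05 and that any one significant result counts. Under independence: 1 − 0.95² = 9.75% for two and 1 − 0.95⁴ = 18.55% for four. Simulated t-tests at 17 per group (200,000 runs, equal correlation r between comparisons):

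| r | two comparisons | four comparisons |
|---|---|---|
| 0 | 9.7% | 18.5% |
| 0.5 | 9.0% | 15.7% |
| 0.7 | 8.3% | 13.3% |
| 0.9 | about 7% | about 9.5% |

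**6. What a fixed order would cost.** If ODI is tested first and NPRS only after a significant ODI, the chance of confirming both equals the chance that both are significant at .05. With d = 0.991 on both outcomes this is 64.1% at r = 0, rising to 74.8% at r = 0.9. If NPRS has an illustrative d of 0.5, it is about 24–29%.

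No effect size or correlation in steps 2 to 6 comes from the protocol; all are assumptions.

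**The case against.** The strongest reply is that the documents say more than section 4.0 does. Section 2.0 states a directional between-group hypothesis, section 12.1 points to disability, and the ODI is the disability questionnaire. A reader might otherwise infer that no contrast exists at all, or that the power statement attaches to nothing. The documents do not support that: leaderboard versus packet on disability is a fair inference. It remains an inference, without a visit, form of comparison, test or effect size.

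Second, section 9.1 helps. A reader might count all five post-baseline visits, giving ten comparisons and 1 − 0.95¹⁰ = 40.1% under independence. The 8-month date points away from months 12 to 24, so that count is too high. The date does not choose between weeks 3 and 6. It is also attached to completion of the study, which does not fit a 24-month follow-up in the same section.

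Third, section 17.1 plans estimates and intervals, and no any-one-wins rule appears anywhere. That is right, and the false-positive figures are therefore illustrations and not error rates of this plan. But if the analysis is estimation only, the stated alpha and power have no declared use. The missing definition remains on either reading.

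**Conclusion.** The point holds. The endpoint as written is not an outcome. ODI and NPRS are unranked, no primary visit is named, the form of the comparison and the success rule are absent, and the 80% power at 17 per group has no stated inputs. This conclusion rests on the text alone and needs none of the calculations.

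The size is conditional. Under an assumed any-one-wins rule at .05, the false-positive chance is about 7–10% for two comparisons and 9–19% for four, over correlations 0.9 to 0. For a simple two-sided t-test, 17 per group gives 80% power only for a standardized difference near 0.99. A reader might infer that the trial is underpowered. The documents do not show this, because the intended difference and SD are not given; nor do they show that 34 completers are enough.

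**What to change.** **Sections 4.0 and 17.1.** Replace the endpoint sentence in 4.0 and the matching words in 17.1 with one primary comparison. For example: *The primary endpoint is ODI at 6 weeks, compared between groups by a linear model adjusted for baseline ODI, two-sided alpha .05. NPRS at 6 weeks, analysed the same way, is tested second, only if ODI is significant. Other visits and outcomes, including adherence and ultrasound, are reported as estimates with 95% CIs.* ODI first fits the disability basis in 12.1, but the choice and order are the investigators'. A stated co-primary or split-alpha rule would also close the gap, provided the plan says what the 80% then refers to.

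**Study Summary.** Align the primary objective with that choice.

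**Section 12.2.** Tie the 80% to the named comparison, with its effect size, SD, test and sidedness. If those inputs do not support 80% at 17 per group, restate the power.

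**Section 9.1.** Say that the 8 months refers to the 6-week analysis.

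**Cost.** The changes are to wording, and a fixed test order adds nothing to the sample size for multiplicity. The price is in the claims. Pain can be confirmed only if ODI is significant: the chance of confirming both is 64–75% if both outcomes have d = 0.99, and about 24–29% if NPRS has d = 0.5. Adherence, which has its own directional hypothesis, becomes supportive, as do the ultrasound and 12- to 24-month results.

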### **Study Intervention/Investigational Agent**

5.1 There will be two groups in this study, the leaderboard group, and the take-home packet group. The leaderboard group and the take-home packet group will be completing the same exercise program throughout the 6-weeks. The exercises included the PBP, TESP (left and right side), FESP (left and right side), dead bug and bird dog exercise until discontinuation. The exercises will increase with repetitions every two weeks and that outline is listed below in procedures involved. The leaderboard group will have on demand video access to the exercises and the take-home packet group will have a take-home packet. The leaderboard group will also be receiving weekly leaderboards of average and top exercise durations of the leaderboard group participants. The audio description of exercise in the on-demand video group is the same script as the written description in the take-home packet. Both groups will be completing the same questionnaires which are described later.

### **6.0 Procedures Involved\***

6.1 This 6-week randomized controlled trial includes two groups completing at-home exercise program of the PBP, TESP (left and right side), FESP (left and right side), dead bug and bird dog exercise until discontinuation. The exercises will be

completed 3 times a week for 6 weeks. The leaderboard group will be receiving on demand videos of the exercises and weekly leaderboards of exercise duration. The weekly leaderboards are what make the leaderboard group competitive and gamified. Competition is created with the comparison between ones hold times to top hold times and average hold times in the group as well as reference values. The take-home exercise packet group will receive take home at-home exercise packet. The participants in both groups will complete the first exercise session and last exercise session in the READY laboratory. The other exercise sessions will be completed on the participant's own. The take-home exercise packet group will be using a take-home packet to refer to the exercises (PBP, TESP, FESP, dead bug and bird dog) they are to complete within the 6-weeks. The leaderboard group will be using on-demand videos to refer to the exercises (PBP, TESP, FESP, dead bug and bird dog) they are to complete within the 6-weeks. The leaderboard group will also be receiving weekly leaderboards of average and top exercise durations of the leaderboard group participants.

Participants will be randomized into the two separate groups using a random number generator and allocation will be concealed in opaque envelopes prior to data collection.

Weeks 1 to 2 individuals will complete 3 exercise sessions of 1 repetition of the 7 exercises.

Weeks 3 to 4 individuals will complete 3 exercise sessions of 2 repetitions of the 7 exercises

Weeks 5 to 6 individuals will complete 3 exercise sessions of 3 repetitions of the 7 exercises.

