## **25.0 Resources Available**

25.1 Due to the number of individuals in the university area and surrounding East Orlando community, recruiting, and enrolling 40 healthy subjects within a 4-month timeframe is very feasible. Out of the number of students, faculty, and staff on the main campus in general, we do not foresee an issue with recruitment.

The PI will be the primary contributor in conducting and completing the research.

The Rehabilitation Athletic assessment & Dynamic Imaging Laboratory is located in the Education Complex on the first floor in Room 174. It is a 7x11 foot space equipped with a GE NextGen Logiq e ultrasound unit, Delsys Trigno Avanti Electromyography+Inertial Measurement Unit+Biofeedback System, hand-held dynamometer, digital inclinometer, adjustable high/low treatment table, and rehabilitation and exercise equipment.

There is an automated external defibrillator (AED) located just outside of the READY Lab in the hallway leading to Room 174 and a first aid kit for any small wounds. The PI is also a certified and licensed Athletic Trainer in the state of Florida, as well an American Red Cross Certified Professional Rescuer in CPR/AED and First Aid. We are also located near Student Health and CAPS, if the subject happens to be a UCF student, and study team members are also trained to call 911 in case

of any emergency. Any events that would result in an emergency would be reported to the IRB appropriately. All study team members have thoroughly read and studied the protocol and are up to date on all appropriate training. They have met and discussed with the PI their role and clearly described and agreed to that designated in the protocol. They were given time to answer questions to insure they had time to fully understand or clear up any misunderstanding prior to contact with any subjects or commencement of the protocol.

N/A

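### Section 6.1 leaves the random sequence and the time of envelope opening unspecified, and no baseline adjustment is planned: restrict the list, open late, and adjust for baseline NPRS and ODI

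*Combined protocol and SAP*

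**What the plan says.** The method of allocation takes up one sentence of section 6.1. Its first half reads "Participants will be randomized into the two separate groups using a random number generator". On concealment, its second half says that "allocation will be concealed in opaque envelopes prior to data collection". The document does not mention blocks, strata, a fixed-total list, who prepares the envelopes, whether they are numbered, or when each is opened.

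Section 12.2 sets the target. "A total of 34 individuals (17 per group) will be adequate with 80% power at an alpha level of .05", and the attrition allowance is one "which results in a total sample size of 40 individuals, 20 in each group".

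Four other places bear on the point:
- Section 10.2 admits people on a self-reported history of low back pain (an episode in the last 6 months, or more than 3 in 3 years). No minimum current score is required.
- Under Consent and Screening, the NPRS and ODI are completed in REDCap. Exercise teaching, 60 ultrasound images and the first exercise bout follow. The first arm-specific step with a stated time is the emailing of video links to the leaderboard group, after that bout (Protocol Description and Participant Reporting).
- Section 17.1 plans mean differences, confidence intervals and effect sizes for the questionnaires, and names no model or baseline covariate.
- Section 25.1 says "The PI will be the primary contributor in conducting and completing the research".

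**The concern.** Three things are left open, and each can be closed cheaply before enrolment starts.

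First, nothing in section 6.1 secures the equal groups that section 12 assumes.

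Second, change in pain is part of the primary objective, and a person who scores 0 at entry cannot improve on that score. If such people fall unevenly between the arms, the comparison of change is distorted. Neither the allocation nor the stated analysis protects against this.

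Third, if an envelope is opened early in the first visit, the teaching, image acquisition and first hold times are all done with the arm known. The person doing them may also be the one who enrols. These are the baseline measures against which change is judged.

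**Working it through.** **The plan's own figure.** 34 / (1 − 0.15) = 40.0 and 17 / 0.85 = 20 per group, so the 40 reproduces. The 34 cannot be checked, because no effect size, SD or test is given. For the power figures below I take the effect that 17 per group would detect with 80% power at two-sided alpha 0.05 (sidedness is assumed): d = (1.960 + 0.842) × √(2/17) = 0.96 by the normal approximation, or 0.99 by the t-test.

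**Group sizes, if randomisation is simple.** X ~ Binomial(40, 0.5).
- P(exactly 20/20) = C(40,20) / 2^40 = 12.5%
- P(18/22 or worse) = 63.6%
- P(15/25 or worse) = 15.4%
- Central 95% range for one arm: 14 to 26

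**What unequal sizes cost.** Power = Φ(d / √(1/n1 + 1/n2) − 1.960), with d = 0.961 and 15% lost from each arm.

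| Randomised | Completers | Power |
|---|---|---|
| 20/20 | 17.0/17.0 | 80.0% |
| 18/22 | 15.3/18.7 | 79.6% |
| 16/24 | 13.6/20.4 | 78.4% |
| 14/26 | 11.9/22.1 | 76.2% |

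For 14/26: √(1/11.9 + 1/22.1) = 0.3596; 0.961 / 0.3596 = 2.673; Φ(2.673 − 1.960) = 0.762. Averaged over random splits of 34 completers (t-test), power is 78.8%.

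**Baseline pain, even with an exact 20/20 split.** Assume 12 of 40 have NPRS 0. The number in one arm is hypergeometric: P(k) = C(12,k) × C(28,20−k) / C(40,20).
- P(5) = 0.2151, P(6) = 0.2689, P(7) = 0.2151
- P(8 v 4 or worse) = 1 − 0.6992 = 30.1%

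The document does not give the number who are pain-free. The chance of a difference of 4 or more is 23.5% for 8 such people, 33.3% for 16 and 34.3% for 20.

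For any continuous baseline score, the standard error of the difference in SD units is √(2/20) = 0.316. So P(difference above 0.5 SD) = 2 × (1 − Φ(0.5/0.316)) = 11.4%. In simulation (20,000 runs each) it was 11.5% for a fixed 20/20 list and 11.9% for simple randomisation. Fixing the sizes alone therefore does almost nothing for baseline balance.

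**What stratified blocks would do.**
- With blocks of 4 in two strata cut at the median of a normal score (an assumption), the SD of the baseline difference falls from 0.32 to 0.20. The chance of a gap above 0.5 SD falls to about 1%. Sizes are exactly 20/20 in 63% of runs and never worse than 18/22.
- With mixed blocks of 2 and 4, stratified by NPRS 0 v 1 or more, exact 20/20 occurs in about 80% of runs when the pain-free number is fixed at 8, 12, 16 or 20. It occurs in about 65% when each person has a 30% chance of being pain-free. The split can still reach 18/22.

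**Predictability.** Suppose someone always guesses the arm with fewer allocations so far, within stratum where there are strata. The guess is right 50% of the time under simple randomisation, about 59% under a fixed 20/20 shuffle, and about 71% under stratified blocks of 2 and 4.

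**The case against.** The strongest reply is that section 6.1 is silent, not wrong. A random number generator can shuffle 20 slips for each arm into envelopes before the trial begins. Sections 12.1, 12.2 and 17.1 all give 20 per group, which fits that reading at least as well as coin-tossing. This stands. A reader might infer that the trial uses unrestricted allocation, but the document does not say so, and the 12.5% applies only if it does.

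The reply has force on three further points:
- A reader might infer that unequal arms undermine the 80% power. They do not: the loss is about 1 point on average and under 4 points at 14/26.
- A reader might infer that stratified blocks would guarantee both equal sizes and baseline balance. They bring the sizes close and reduce imbalance. Small blocks also make the next arm easier to guess where the arms are visible to the researcher, and late opening does not prevent guessing from past allocations.
- Nothing in the document shows that current pain is the strongest predictor of outcome. Section 12.1 bases the sample size on disability, which a pain stratum balances only as far as the two scores correlate.

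On concealment, opaque envelopes are specified and section 25.1 also mentions other team members with designated roles. The text does not show that concealment fails or that allocation is known early.

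The reply does not answer two things. Even the favourable fixed-list reading leaves baseline pain to chance with no stated adjustment, and the time of opening is unstated under every reading.

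**Conclusion.** The point holds as a gap in specification with a modest but real consequence. The sequence type and the opening time are not stated. If allocation is simple, 20/20 arises in 12.5% of trials, at a cost of about 1 to 4 points of power for splits between 16/24 and 14/26. That rests on the implied effect and a two-sided test.

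Baseline imbalance is the weightier half, because it applies to any unstratified list: about 30% for a split of 8 v 4 or worse if 12 are pain-free, with a range of 24% to 34% for 8 to 20 people. The number who are pain-free is an assumption. Baseline adjustment is the main remedy, since it deals with both pain and disability. Stratification is a useful extra but not a requirement. The change should be made before the first enrolment, because the list and the order of events cannot be repaired afterwards. The point does not by itself invalidate the design.

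**What to change.** Replace the allocation sentence in section 6.1 with wording such as:

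*A computer-generated 1:1 list, restricted by [a fixed total of 20 per group / permuted blocks of varying size, none of size 2, not disclosed to the enrolling researcher], is prepared in advance by a person who does not enrol participants. It is held in REDCap or in sealed, sequentially numbered opaque envelopes. Allocation is revealed only after the baseline questionnaires, ultrasound images and first laboratory exercise session are complete.*

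If the sponsor chooses blocks, the list may be stratified by baseline NPRS (0 v 1 or more), with the cut-point fixed in advance.

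Add to section 17.1 that the group comparisons of NPRS and ODI are adjusted for the baseline value of the same score (analysis of covariance), and for the stratum if one is used.

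Late opening fits the existing visit. Both arms do the same exercises, the baseline scores are already in REDCap, and the video links go out after the first session. The document does not say when the packet is handed over, so that step should be placed after the reveal as well.

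**Cost.** A few sentences, a new list and one person outside enrolment. Restricted lists are somewhat more predictable when the arms are visible, which is why blocks of 2 should be avoided and block sizes kept hidden. Blocks do not guarantee equality. With two strata, each can end out of balance by half the largest block. Blocks of up to 4 therefore allow a difference of 2 + 2 = 4 (18/22), and blocks of up to 6 allow 3 + 3 = 6 (17/23). A fixed list guarantees 20/20 only if all 40 are enrolled, and it does not balance baseline pain.
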